5 INVESTIGATIONAL PRODUCT

5.1 Identification of Investigational Product

Technetium Tc 99m tilmanocept was approved under the brand name Lymphoseek in the USA by the FDA in year 2013 NDA number 202207 as radio-inaging agent. Technetium Tc 99m tilmanocept is a scintigraphic imaging radiotracer that binds to CD206 (mannose receptor) on the surface of macrophages and other inflammatory cells. It is comprised of multiple units of DTPA (diethylenetriaminepentaacetic acid) and mannose, each synthetically attached to a 10 kDa dextran backbone (Figure 1). The mannose acts as a substrate for the receptor and the DTPA serves as a chelating agent for labeling with Tc 99m. Tilmanocept has a diameter of about 7 nm, which permits enhanced diffusion into lymph nodes and blood capillaries.

[figure not shown]

Figure 1 Tc 99m tilmanocept and the Mannose Receptor

5.2 Investigational Product Dosage and Administration

Tc 99m tilmanocept will be administered through an IV route of injection. A 150-mcg dose containing 10 mCi of Tc 99m in 3 mL will be delivered using 1 syringe. The dose will be injected as a slow push into the IV catheter. At the completion of the injection, a 10-mL sterile normal saline flush will be administered. The preferred site of IV placement will be the left or right antecubital vein.

The administered dose will be \pm 20% of the tilmanocept mass dose and radiolabel mCi dose.

5.3 Treatment Assignment

Subjects will receive the study-defined dose of 150 mcg tilmanocept radiolabeled with 10 mCi of Tc99m. Subjects will undergo drug administration and imaging at the following 4 timepoints:

- 1. Day 0 (Visit 2)
- 2. 5 ± 1 weeks after the initiation of new anti-TNF α bDMARD therapeutic regimen (Visit 4)

5.4 Packaging and Labeling

Tilmanocept cartons ready for radiolabeling will be shipped and stored at the study-assigned radiopharmacy. Tilmanocept is provided in a vial. Vials are packaged as a kit. A carton (kit) contains 5 vials of tilmanocept.

A detailed radiolabeling protocol will be provided to each radiopharmacy with instructions on how to radiolabel the vials and prepare the final tilmanocept product for injection. Quality Control worksheets will also be completed.

5.5 Drug Logistics and Investigational Product Accountability

The investigator (or designated personnel) will confirm receipt of the investigational product in writing and will use the investigational product only within the framework of this clinical study and in accordance with this study protocol. For each subject, he/she will keep a record of the investigational product dispensed and store all other forms that accompanied the delivery of the radiolabeled product to the clinical site. These documents are to be filed in the investigator site file. Overall drug accountability and reconciliation will be completed by the sponsor or its representative. A list of investigational product vials and other materials that were returned, or destroyed, must be recorded and signed by the PI or an appropriately qualified designee. An overall accountability and reconciliation form of the investigational product will be prepared and completed. If there are any discrepancies, they must be investigated and their resolution documented. All unused study kits will be destroyed in accordance with institutional destruction procedures.

6 THERAPIES OTHER THAN INVESTIGATIONAL PRODUCT

6.1 Prior and Concomitant Therapy

All medications taken 30 days prior to Tc 99m tilmanocept injection through the post-injection safety follow-up must be documented and maintained at a stable dose according to the inclusion criteria. The subject's complete history of RA treatments will also be collected.

6.2 Post-Study Therapy

There are no post-study therapy restrictions.

7 STUDY PROCEDURES

7.1 Schedule of Evaluations

A schedule of evaluations is provided in the Schedule of Study Events (see Appendix 1). Visits 7 and 9 have been eliminated per Protocol Amendment 4. For continuity, visits have not been renumbered (i.e., Visit 6 is followed by Visit 8).

7.2 Visit Description

7.2.1 Visit 1, Screening (Day -30 to Day -1)

- Preliminary review of inclusion and exclusion criteria
- Obtain signed informed consent for study participation
- Allocation of unique subject number; this number will be used to document the subject data in the case report forms (CRFs) and enrollment log
- Demography date of birth, biological sex, race
- Medical and surgical history all relevant prior medical and surgical conditions, which may include RA family history, and RA treatment history, will be recorded in the CRF. Documented medical conditions will also note the month and year of onset if the condition is still active.
- Concomitant medications (within 30 days before injection).
- Vital signs (body temperature, heart rate, blood pressure, and respiratory rate after at least 1 minute in a resting position)
- Physical examination will include an assessment of height, weight, and an examination of general appearance, skin, eyes, ears, nose, throat, head and neck (including thyroid), lungs, heart, abdomen, lymph nodes, musculoskeletal, and nervous system. Any clinically relevant finding is to be documented as a baseline finding. Physical exams that are conducted as standard of care prior to signing informed consent may be used if they are performed within 30 days of injection.
- Clinical laboratory tests study subjects will have blood obtained for hematology, chemistry, and an RA panel (Table 4)
- Urine collection for routine analysis
- Urine pregnancy test for women of childbearing potential. Females of childbearing potential are defined as women that are not surgically sterile (hysterectomy or bilateral oophorectomy) nor postmenopausal for at least 1 year prior to screening. Women who are not of childbearing potential will not require a pregnancy test.
- RA Evaluations: Swollen and tender joints will be identified and documented during physical examination as established by the 2010 ACR/EULAR Classification Criteria and DAS28. A HAQDI[©] assessment will be completed to assess quality of life related to health. A CDAI assessment will be used to quantify and track disease activity. A review of the subject's RA history including previous treatments, date of symptom onset, and date of diagnosis will also be performed.

• Widespread Pain Index (WPI) Assessment

Changes in health occurring after consent and prior to the day of injection will be added to the subject's medical history unless related to a study procedure.

7.2.2 Visit 2, Baseline (Day 0; Drug administration/Imaging)

All subjects will be assessed for adverse events in an ongoing manner from the day of injection through the end of participation.

7.2.2.1 Before Administration of Tc 99m Tilmanocept

The following procedures will be completed for all subjects on the day of injection prior to the administration of Tc 99m tilmanocept:

- A urine pregnancy test for women of childbearing potential. Females of childbearing potential are defined as women that are not surgically sterile (hysterectomy or bilateral oophorectomy) nor postmenopausal for at least 1 year prior to screening. Women who are not of childbearing potential will not require a pregnancy test.
- Assessment of adverse events
- Concomitant medication review
- Vital signs after at least 1 minute in a resting position (body temperature, heart rate, blood pressure, and respiratory rate) within 30 minutes prior to administration of Tc 99m tilmanocept

7.2.2.2 Administration of Tc 99m Tilmanocept

IV administration of Tc 99m tilmanocept will be at study time 00:00. The preferred site of IV placement will be the left or right antecubital vein.

The pre-filled syringe will be connected to a catheter for a slow push injection. At the completion of the injection, a 10-mL sterile normal saline flush will be administered. The IV administration will be performed in the nuclear medicine department by an onsite Certified Nuclear Medicine Technologist or Nuclear Medicine Physician. Subjects will be continuously monitored for adverse events.

7.2.2.3 0 to 30 Minutes After Tc 99m Tilmanocept Administration

- Assessment of adverse events
- Vital signs after at least 1 minute in a resting position (body temperature, heart rate, blood pressure, and respiratory rate)

7.2.2.4 60 to 75 Minutes After Tc 99m Tilmanocept Administration

- Assessment of adverse events
- Image acquisition: planar scan of bilateral hands and wrists
- Clinical labs (within 60 minutes after the completion of imaging)
- Urinalysis (within 60 minutes after the completion of imaging)

Upon the completion of all Visit 2 procedures, subjects will initiate their new anti-TNFa bDMARD treatment regimen. The exact agent, dose, start date, and planned dosing frequency will be documented. For each subsequent administration, the following details will be documented:

- 1. Administration start time
- 2. Administration end time
- 3. Total volume injected
- 4. Total dose administered

7.2.3 Visit 3 (Day 5 ± 3 ; Follow-up Telephone Safety Assessment)

- Review of concomitant medications
- Assessment of adverse events

7.2.4 Visit 4 (Week 5 ± 1 ; Tc 99m Tilmanocept Administration, Imaging, and Clinical Assessments)

7.2.4.1 Before Tc 99m Tilmanocept Administration (0-7 days pre-injection)

The following procedures will be completed for all subjects within 7 days prior to the administration of Tc 99m tilmanocept:

- CDAI
- DAS28 (note: associated labs occur after imaging)
- HAQ-DI©
- WPI

7.2.4.2 Before Tc 99m Tilmanocept Administration (day of injection)

The following procedures will be completed for all subjects on the day of injection prior to the administration of Tc 99m tilmanocept:

- A urine pregnancy test for women of childbearing potential. Females of childbearing potential are defined as women that are not surgically sterile (hysterectomy or bilateral oophorectomy) nor postmenopausal for at least 1 year prior to screening. Women who are not of childbearing potential will not require a pregnancy test.
- Assessment of adverse events
- Concomitant medication review
- Vital signs after at least 1 minute in a resting position (body temperature, heart rate, blood pressure, and respiratory rate) within 30 minutes prior to administration of Tc 99m tilmanocept

7.2.4.3 Tc 99m Tilmanocept Administration

IV administration of Tc 99m tilmanocept will be at study time 00:00. The preferred site of IV placement will be the left or right antecubital vein.

The filled syringe will be connected to a catheter for a slow push injection. At the completion of the injection, a 10-mL sterile normal saline flush will be administered. The IV administration will be performed in the nuclear medicine department by an onsite Certified Nuclear Medicine Technologist or Nuclear Medicine Physician. Subjects will be continuously monitored for adverse events.

7.2.4.4 0 to 30 Minutes After Tc 99m Tilmanocept Administration

- Assessment of adverse events
- Vital signs after at least 1 minute in a resting position (body temperature, heart rate, blood pressure, and respiratory rate)

7.2.4.5 60 to 75 Minutes After Tc 99m Tilmanocept Administration

- Assessment of adverse events
- Image acquisition: planar scan of bilateral hands and wrists
- Clinical labs (within 60 minutes after the completion of imaging)
- Urinalysis (within 60 minutes after the completion of imaging)
- RA labs (within 60 minutes after the completion of imaging)

7.2.5 Visit 5 (5 ± 3 Days After Visit 4; Follow-up Telephone Safety Assessment)

- Review of concomitant medications
- Assessment of adverse events

7.2.6 Visit 6 (Week 12 \pm 1; Clinical Assessments)

The following procedures will be completed for all subjects at Week 12 ± 1 :

- CDAI
- DAS28
- HAQ-DI[©]
- WPI
- RA labs
- Assessment of adverse events
- Concomitant medication review

7.2.7 Visit 8 (Week 24 \pm 1; Clinical Assessments; note that Visit 7 will not be conducted per this amendment)

7.2.7.1 Before Tc 99m Tilmanocept Administration (0-7 days pre-injection)

The following procedures will be completed for all subjects at Week 24 ± 1 :

- CDAI
- DAS28
- HAQ-DI©
- WPI
- RA labs
- Assessment of adverse events
- Concomitant medication review

8 PROCEDURES AND VARIABLES

8.1 Population Characteristics

8.1.1 Demographic and Other Baseline Characteristics

Based on response to anti-TNF α bDMARD therapy, 198 to 672 evaluable subjects may be enrolled. Subjects will be men and women \geq 18 years of age with evidence of active RA. A subject is considered evaluable if he/she meets the criteria for the analysis population and has the data necessary for computing the primary endpoint. There will be no exclusions based on specific subgroups (e.g., subjects with various demographic characteristics; disease severity, duration, or response to prior therapies; co-existing conditions; genetic variants; concomitant medications; or prior treatment with non-TNF biologic therapies).

8.1.2 Medical and Surgical History

Relevant medical, rheumatological, and surgical histories will be obtained on all study subjects. As part of the medical history, the date of the last spontaneous menstruation will be recorded if childbearing potential is not excluded by surgical sterilization. Rheumatological history will include date of RA diagnosis as well as the timing, dose, administration frequency, and administration route (when available) of all RA-specific drugs.

8.2 Tc 99m Tilmanocept Administration

Tc 99m tilmanocept must be ordered from the study-assigned radiopharmacy once the subject has been scheduled for IV administration and imaging. The preferred site of IV placement will be the left or right antecubital vein. The filled syringe will be connected to a catheter for a slow push injection. Immediately after the completion of the injection, a 10 mL sterile normal saline flush will be administered. Injection of Tc 99m tilmanocept will be at study time 0:00.

8.3 Rheumatological Assessments

8.3.1 2010 ACR/EULAR Classification Criteria

All subjects will be evaluated at screening using the 2010 ACR/EULAR Classification Criteria as part of eligibility and inclusion (Aletaha 2010). The 2010 ACR/EULAR Classification Criteria includes 4 components: number and site of involved joints, serologic abnormality, elevated acute-phase response and symptom duration. See Appendix 2 for details. A total score of 6 or higher (out of a possible 10) combined with clinical synovitis not better explained by another disease confirms a diagnosis of "definite RA."

8.3.2 DAS28 Evaluation

Subjects will be evaluated for the DAS28 (Prevoo 1995) at the following timepoints: screening (Day -30 to -1), Visit 4 (5 \pm 1 weeks post-initiation of new anti-TNF α bDMARD), Visit 6 (12 \pm 1 weeks post-initiation of new anti-TNF α bDMARD), and Visit 8 (24 \pm 1 weeks post-

initiation of new anti-TNFα bDMARD). DAS28 evaluations may be completed up to 30 days before imaging Visit 2 and up to 7 days before imaging Visits 4, 6, and 8.

DAS28 is calculated from 4 components: Tender Joint Count (TJC), Swollen Joint Count (SJC), visual analogue scale (VAS) of the subject's global health, and the laboratory parameter erythrocyte sedimentation rate (ESR), such that:

$$DAS28 = 0.56\sqrt{TJC} + 0.28\sqrt{SJC} + 0.7\ln(ESR) + 0.014(VAS)$$

A DAS28 score of higher than 5.1 is indicative of high disease activity whereas a DAS28 below 3.2 indicates low disease activity. A subject with a DAS28 lower than 2.6 is considered to be in remission. For consistent scoring, the following calculator should be utilized: https://qxmd.com/calculate/. See Appendix 3 for details.

8.3.3 CDAI

Subjects will be evaluated for disease activity using the Clinical Disease Activity Index (Aletaha 2009). CDAI will be collected a total of 4 times per subject (screening, Visit 4, Visit 6, and Visit 8). The CDAI evaluation may be completed up to 30 days before imaging Visit 2 and up to 7 days before imaging Visits 4, 6, and 8. This metric is calculated as the sum of 4 components: TJC, SJC, patient global assessment of disease activity, and provider global assessment of disease activity. A CDAI score of 0.0 to 2.8 is indicative of disease remission; 2.9 to 10.0 of low activity, 10.1 to 22.0 of moderate activity, and 22.1 to 76.0 of high activity. See Appendix 4 for details.

8.3.4 ACR Response Criteria

Subjects will be evaluated using the ACR Response Criteria (Felson 1995). ACR Response is derived from 6 possible parameters: swollen/tender joint count, patient assessment, physician assessment, pain scale, disability/functionality questionnaire, and acute phase reactant (ESR/CRP). Response is reported as percent (%) improvement from baseline to a later timepoint. In this case, a total of 2 timepoints will be evaluated per subject (Visits 6 and 8).

Percent improvement is defined as a combination of reductions in swollen and tender joint counts as well as improvement in at least at least 3 of the other parameters (patient assessment, physician assessment, pain scale, disability/functionality questionnaire, and acute phase reactant [ESR]). An ACR20 indicates that 20% improvement is observed in tender and swollen joint counts as well as 20% improvement in at least 3 of the other 5 criteria. An ACR50 indicates that 50% improvement is observed in tender and swollen joint counts as well as 50% improvement in at least 3 of the other 5 criteria. An ACR70 indicates that 70% improvement is observed in tender and swollen joint counts as well as 20% improvement in at least 3 of the other 5 criteria. See Appendix 5 for details.

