Appendix 5 ACR Response Criteria

ACR Response Criteria

The ACR (American College of Rheumatology) Criteria is a standard criteria to measure the effectiveness of various arthritis medications or treatments in clinical trials for Rheumatoid Arthritis. The ACR is used to maximally discrimate effective treatment for placebo treatment in clinical trials. The ACR criteria is indicated as ACR 20, ACR 50, or ACR 70. The ACR is reported as % improvement, comparing disease activity at two discrete time points (usually baseline and post-baseline comparison).

- ACR20 is ≥ 20% improvement
- ACR50 is ≥ 50% improvement
 - ACR50 reponders include ACR20 responders
- ACR70 is \geq 70% improvement
 - o ACR70 reponders include ACR20 & ACR50 responders

Definition

The ACR Criteria is a dichotomous variable with a positive (=responder) or negative (=non-reponder) outcome.

The ACR Criteria measures improvement in tender and swollen joint counts in improvement in at least three or the following parameters:

- 1. Patient assessment
- 2. Physician assessment
- 3. Pain scale
- 4. Disability/functional questionnaire
- 5. Acute phase reactant (ESR or CRP)

ACR 20 has a positive outcome if 20% improvement in tender and swollen joint counts were achieved as well as 20% improvement in at least three of the other five criteria.

ACR 50 has a positive outcome if 50% improvement in tender and swollen joint counts were achieved as well as 50% improvement in at least three of the other five criteria.

ACR 70 has a positive outcome if 70% improvement in tender and swollen joint counts were achieved as well as 70% improvement in at least three of the other five criteria.

Confidential Page 84 of 89

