4.1.1.2 Clinical Assessments

ACR Response is derived through a combination of reductions from baseline in swollen or tender joint counts as well as improvement from baseline in at least 3 of the other parameters (patient assessment, physician assessment, pain scale, disability/functionality questionnaire, and acute phase reactant [ESR]). This study will evaluate the following three levels of ACR Response:

• ACR20: An ACR20 indicates that 20% improvement is observed in tender and swollen joint counts as well as 20% improvement in at least 3 of the other 5 criteria.

- ACR50: An ACR50 indicates that 50% improvement is observed in tender and swollen joint counts as well as 50% improvement in at least 3 of the other 5 criteria.
- ACR70: An ACR70 indicates that 70% improvement is observed in tender and swollen joint counts as well as 70% improvement in at least 3 of the other 5 criteria.

Each patient will be classified as a yes or a no for whether they meet each of the above ACR Response Criteria at each of the applicable post-baseline time points. Note that the above criteria are nested, such that if a patient is a yes for ACR70 at a given time point, then the patient is also a yes for ACR50 and ACR20 for that same time point.

A patient will be classified as improved on the CDAI depending on the baseline score as follows:

- If the baseline value is greater than 22, a reduction of more than 12 will be classified as improved. Otherwise, the patient is not improved.
- If the baseline value is between 10 and 22 (inclusive) a decrease of more than 6 will classified as improved. Otherwise, the patient is not improved.
- If the baseline value is less than 10, a decrease of more than 1 will be classified as improved. Otherwise the patient is not improved.

A patient will be classified as improved on the DAS28 with a score change of greater than 1.2.

A decrease of at least 0.22 in the HAQ-DI will be classified as improved. Otherwise, the patient is not improved on the HAQ-DI.

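### Protocol 8.3.4 defines ACR70 with a 20% threshold for the other criteria, against 70% in Appendix 5 and the SAP, so an ACR70 responder need not be an ACR50 responder

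*Protocol*

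**What the plan says.** The ACR response levels are defined in three places.

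- **Protocol 8.3.4** gives matched thresholds for the two lower levels. Its ACR20 sentence reads "An ACR20 indicates that 20% improvement is observed in tender and swollen joint counts as well as 20% improvement in at least 3"; its ACR50 sentence reads "An ACR50 indicates that 50% improvement is observed in tender and swollen joint counts as well as 50% improvement in at least 3". The top level is not matched: "An ACR70 indicates that 70% improvement is observed in tender and swollen joint counts as well as 20% improvement". Throughout, the second figure must be met by three or more of the five non-joint criteria. The section then refers the reader to Appendix 5 for details.
- **Protocol Appendix 5** reads: "ACR 70 has a positive outcome if 70% improvement in tender and swollen joint counts were achieved as well as 70% improvement", with the same count of three or more. On nesting it says: "ACR70 reponders include ACR20 & ACR50 responders".
- **SAP 4.1.1.2** reads: "An ACR70 indicates that 70% improvement is observed in tender and swollen joint counts as well as 70% improvement in at least 3". It adds that the levels are nested, so that a yes for ACR70 at a time point is also a yes for ACR50 and ACR20 at that time point.

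ACR20, ACR50 and ACR70 at weeks 12 and 24 are listed as secondary response variables in Protocol 9.3.3 and SAP 4.1.4. Protocol 9.5.3.3 and SAP 4.2.3 plan a frequency table that counts each patient once, at the highest level attained.

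**The concern.** Section 8.3.4 is where the protocol body defines the response criteria. Its ACR70 sentence carries the ACR20 threshold for the five non-joint criteria. It therefore conflicts with the protocol's own appendix, with the SAP, and with the nesting that both of those state.

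An analyst working from section 8.3.4 would label as ACR70 some patients whose improvement outside the joint counts meets only the ACR20 standard. The affected outputs would be:

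- the ACR70 part of the concordance tables (SAP Tables 11 to 28);
- the highest-level frequency table (Tables 9 and 10);
- Figure 3;
- the ACR status shown in Listings 18 and 30.

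The frequency table has a further problem. A patient who is ACR70 but not ACR50 sits in the ACR70 column, so the ACR50 and ACR70 columns together would exceed the number of patients who meet ACR50. The table would then disagree with the ACR50 status used as the primary reference standard.

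**Working it through.** No sample size, power or alpha figure depends on ACR70, so there is no stated figure to reproduce. The check is one of logic.

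**Thresholds side by side (joint counts / at least three of the other five criteria)**

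| Level | Protocol 8.3.4 | Protocol Appendix 5 | SAP 4.1.1.2 |
|---|---|---|---|
| ACR20 | 20% / 20% | 20% / 20% | 20% / 20% |
| ACR50 | 50% / 50% | 50% / 50% | 50% / 50% |
| ACR70 | 70% / **20%** | 70% / 70% | 70% / 70% |

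**Reduction to two quantities.** Let *J* be the smaller of the improvements in tender and swollen joint counts. Let *K* be the third-largest improvement among the other five criteria. At least three of the five reach a threshold exactly when *K* reaches it. Then:

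- ACR50 (all three places): *J* ≥ 50 and *K* ≥ 50.
- ACR70 by section 8.3.4: *J* ≥ 70 and *K* ≥ 20.
- ACR70 by Appendix 5 and the SAP: *J* ≥ 70 and *K* ≥ 70.

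The two ACR70 rules differ for patients with *J* ≥ 70 and 20 ≤ *K* < 70. Nesting fails under section 8.3.4 for those with *J* ≥ 70 and 20 ≤ *K* < 50. For example, 70% improvement in both joint counts, 20% in three other criteria and 0% in two gives ACR70 yes, ACR50 no, ACR20 yes.

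**Check by enumeration.** Each of the seven components was set to 0, 20, 50 or 70% improvement, giving 4^7 = 16,384 logical profiles. ACR70 needs both joint counts at 70, which is one combination, so the counts follow from the other five criteria.

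- ACR70 by section 8.3.4 (at least three of five at 20 or more; three of the four levels qualify): 10 × 27 × 1 + 5 × 81 × 1 + 243 = 270 + 405 + 243 = **918**.
- ACR70 by Appendix 5 and the SAP (at least three at 70; one of the four levels qualifies): 10 × 1 × 9 + 5 × 1 × 3 + 1 = 90 + 15 + 1 = **106**.
- Of the 918, those also meeting ACR50 (at least three at 50 or more; two of the four levels qualify): 10 × 8 × 4 + 5 × 16 × 2 + 32 = 320 + 160 + 32 = 512.
- ACR70 by section 8.3.4 but not ACR50: 918 − 512 = **406**.
- Classified differently by the two rules: 918 − 106 = **812**.
- ACR70 by section 8.3.4 but not ACR20: 0. ACR50 but not ACR20: 0. ACR70 by Appendix 5 and the SAP but not ACR50: 0.

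These are counts of logical patterns, not patient frequencies. They show which link breaks (ACR70 to ACR50) and that the 70%/70% rule restores it completely.

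**Direction of the effect.** Every 70%/70% responder also meets the section 8.3.4 rule, so applying section 8.3.4 can only add ACR70 responders. In the plan's 2 by 2 table, with the imaging predictions held fixed, the added patients move from cell B to A or from D to C. The row totals T1 and T2 do not change. So PPV = A/T1 can only rise or stay the same, and NPV = D/T2 can only fall or stay the same. Sensitivity and specificity may move either way, because their denominators change too.

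**The case against.** The strongest reply is that this is a one-number slip which the documents nearly resolve themselves. The other two levels in the same paragraph have matched thresholds, the section points to Appendix 5, and the SAP, from which the tables will be programmed, has "70% improvement in at least 3 of the other 5 criteria". If the programmer follows the SAP, the reported ACR70 results will be right. ACR levels are derived from recorded components, so no data are lost and ACR70 can be recalculated at any time. Both co-primary endpoints and the key secondary endpoint use ACR50. Only one of the nesting links fails, and the highest-level table can be produced under either wording.

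Most of this stands, and it limits the weight of the point. It does not remove the contradiction. Neither document says that the appendix or the SAP prevails over the body of the protocol. The SAP introduction ties it to Amendment 3, whereas the current protocol incorporates Amendment 4 (section 7.1), so a reader could take the protocol body as the later statement. The protocol also disagrees with its own appendix, which the SAP cannot cure.

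**Conclusion.** The concern holds. The ACR70 definition in Protocol 8.3.4 is wrong as written. It contradicts Appendix 5 and SAP 4.1.1.2, and it breaks the stated rule that an ACR70 responder is an ACR50 responder. The links from ACR70 to ACR20 and from ACR50 to ACR20 survive.

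The consequence is conditional on section 8.3.4 being applied literally. In that case the ACR70 rate would be overstated or, at best, unchanged, and the ACR70 accuracy measures would be computed against the wrong reference. The size depends on how many patients have at least 70% improvement in both joint counts and 20% to 69% in the third-best other criterion, which the documents do not allow one to estimate.

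The effect is confined to secondary outputs. The co-primary endpoints, the key secondary endpoint and the sample size do not change, provided ACR50 is derived from its own definition. If ACR50 were instead read off the highest level attained, patients like the example above would wrongly enter the primary reference standard as responders. The correction should be made, but it does not put the primary analysis in doubt.

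**What to change.** In the ACR70 sentence of Protocol 8.3.4, change the threshold for the other five criteria from 20% to 70%, to agree with Appendix 5 and SAP 4.1.1.2. The SAP definition needs no change. It would be prudent to confirm in the programming specification that each ACR level is derived from its own thresholds and not from the highest level attained.

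The cost is one number in the next protocol amendment. No data collection, site procedure or sample size changes. The correction should be in place before ACR70 is derived and reported.
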